9.1.2. Unsolicited Adverse Events

Unsolicited AEs that meet the protocol definition of MAAE, NOCD, SAE, AEs leading to delay in dosing of the next vaccine, or AEs leading to termination of vaccine dosing will be captured for the duration of study participation. NOCD are defined as a subset of MAAEs that are specific to new onset of chronic diseases not otherwise suggested or suspected prior to entry into the study. Continuing solicited AEs after 7 days will be captured as unsolicited AEs and followed until stabilization/resolution.

Only treatment emergent adverse events (TEAEs) will be included in summary tables. Percentages will be based upon the number of participants in the Safety analysis set within each treatment group. A participant with 2 or more AEs within the same level of summarization (e.g., SOC or PT) will be counted only once in that level.

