2 STUDY OBJECTIVES AND ENDPOINTS

2.1 Primary Objectives and Endpoints

The primary objective(s) and endpoints are presented in [Table 2-1](#). For estimands, see [Section 7.1](#).

Table 2-1 Primary Objectives and Endpoints

Primary Objectives	Endpoint Description

 To assess the safety and reactogenicity of ARCT-021 compared to placebo for priming vaccination 	
Safety will be evaluated in all participants receiving at least 1 administration of study vaccine (ARCT-021 or placebo) and will be summarized for each vaccination as number and percentage of participants with:
 
 Any unsolicited adverse event (AE) initiating within 28 days after each study vaccine administration, by severity and relationship to study vaccine Any medically attended adverse event (MAAE), new onset of chronic disease (NOCD), AE leading to discontinuation/withdrawal or serious adverse event (SAE) through Early Termination Safety laboratory assessment before and 7 days after each study vaccine administration, by toxicity grade 
Reactogenicity will be evaluated in all participants receiving at least a single administration of study vaccine and will be summarized for each vaccination as number and percentage of participants with:
 
 Any solicited local or systemic AE initiating within 7 days after each study vaccine administration, by toxicity grade

 To assess the neutralizing antibody responses of ARCT-021 compared to placebo for priming vaccination 	
Neutralizing antibody (NAb) responses will be evaluated in all participants receiving at least 1 administration of study vaccine (ARCT-021 or placebo).
 
 Geometric Mean Titer (GMT) measured at all time points Geometric Mean Fold-rise from baseline (GMFR); measured at all time points after baseline (= Day 0) Percentages of participants with ≥ 2- and 4-fold increase in titer from baseline (Seroconversion [SC]); measured at all time points after baseline GMT ratio (ARCT-021/placebo) measured at all time points

 To select the dose and schedule for use in the Phase 3 study in adult participants 	
Safety and reactogenicity data after each priming vaccine administration and immunogenicity responses measured 28 days after each priming vaccination will

Table 2-1 Primary Objectives and Endpoints

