3.1.1 Rationale for Study Design

This Phase 2 study is designed to evaluate the safety and immunogenicity of the ARCT-021 vaccine administered according to 3 different schedules for priming vaccination and to explore one of three vaccines (ARCT-021, ARCT-154, and ARCT-165) versus placebo given as a single dose for booster vaccination in 2 age groups of healthy adults. Younger (≥18 to <56 years) and older (≥56 years) adult participants will be evaluated for their responses to the ARCT-021 vaccine versus placebo. Safety, reactogenicity, and immunogenicity data gathered following the priming vaccination series will be used to select a dose schedule of ARCT-021 that will be used in the next clinical trial in adults. In addition, durability of immune response and the impact of booster dose administration will be investigated within this study design.

The rationale for re-randomization is based on consideration for participants in the study who are assigned to the placebo group in a study under execution in the midst of a global health crisis. Allowing re-enrollment provides these participants access to active study vaccine (ie, ARCT-021) designed to reduce the risk of COVID-19 disease, should this be aligned with the presiding health authority's perspective and with the participant's perception of personal risk. Targeting earliest re-entry after Day 98 allows for approximately 4 months of safety comparison in these participants to provide a meaningful comparator group to those participants assigned to ARCT-021 at the start of the study.

Starting with Version 4.0 of the protocol, multiple booster vaccine candidates will be evaluated in participants who may have previously received ARCT-021 priming vaccination.

Arcturus Therapeutics, Inc.
Protocol ARCT-021-04, Version 6.0

ARCT-021
09 March 2022

ARCT-165 and ARCT-154 are SARS-CoV-2 vaccines that express spike protein from the B.1.351 and D614G strains in contrast to ARCT-021 that expresses spike protein from the Wuhan strain. Safety, tolerability, and immunogenicity data gathered in this study will characterize responses following administration of ARCT-021 vaccine for priming and booster vaccination and will characterize responses following administration of ARCT-154 and ARCT-165 vaccines for booster vaccination. These data will be used to inform future clinical development planning for each of these investigational vaccines.

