For those participants interested in receiving ARCT-021 provided by the Sponsor, an unblinded team member will confirm whether the participant has been assigned to Study Group 4 (placebo) or ARCT-021 (Study Groups 1, 2, or 3). Participants who request to re-enroll in the study but whose treatment assignments are determined to be in Study Groups 1, 2, and 3 will be informed they have already received ARCT-021 and will be advised to continue to remain on the study schedule.

Participants who intend to exit the study to seek approved COVID-19 vaccine will be allowed, after the approval of protocol version 4.0, to receive these vaccines. See [Section 4.2.3](#) for additional guidance.

Participants in Study Group 4 who have not otherwise met withdrawal criteria for study vaccine will sign a consent form, will undergo Early Termination Visit, will be assigned a new participant ID number, and will re-enter the study at Day 0. Re-enrolled participants will be randomly assigned to Study Groups 1, 2, and 3.

Arcturus Therapeutics, Inc.
Protocol ARCT-021-04, Version 6.0

ARCT-021
09 March 2022

Study vaccine will be administered in an observer-blind fashion. Participants will be followed for safety and immunogenicity through 570 days after first vaccination. Participation in the study past Day 388 is optional for participants enrolled in the United States. For participants enrolled in Singapore, participation through the Early Termination Visit is expected. At a subset of clinical sites, all enrolled participants will also undergo blood sampling for evaluation of CMI responses.

Vaccine doses will be assigned as shown in [Synopsis Table 1-1](#) and illustrated in [Synopsis Figure 1-2](#).

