7.6.7 Data Analyses from Re-Enrolled Participants

All safety data collected after active vaccination from Study Group 4 participants who are re-enrolled into Study Groups 1, 2, or 3 (ARCT-021-exposed study groups) will be summarized and presented by dose group and overall separately from those participants who complete the study as originally randomized. Participant level data will be displayed in listings, separately from data in originally randomized.

Immunogenicity data collected after active vaccination from Study Group 4 participants who are re-enrolled into Study Groups 1, 2, or 3 (ARCT 021-exposed study groups) will be listed. This data may be summarized and presented by dose group and overall separately from those participants who complete the study as originally randomized. If summarized, it will be reported in an addendum to the CSR.

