3.1. Overall Study Design and Plan

The overall study design is described below. For the final analysis, data for all participants through early termination will be included.

This is a multiregional, multicenter, Phase 2, randomized, observer-blind study designed to evaluate the safety, reactogenicity, and immunogenicity of the study vaccine in younger and older adult participants. Enrolled participants will be randomly assigned to receive either study vaccine ARCT-021 or placebo (sterile saline) as the priming vaccination series and ARCT-021, ARCT-154, ARCT-165, or placebo as the booster administration.

Approximately 600 participants (300 each in younger [≥ 18 to < 56 years of age in United States or ≥ 21 to < 56 years of age in Singapore] and older [≥ 56 years of age] participants) will be enrolled. At Day 0, participants will be stratified by age and then randomly assigned to one of the 4 groups (3 ARCT-021:1 placebo) to receive 2-doses of study vaccine and/or placebo (see Table 3-1) separated by 28 days and, at Day 208, participants will be randomly assigned to active booster vaccine or placebo for a third (booster) dose of study vaccine given at 180 days after second study vaccination (Day 208). At a subset of clinical sites, all enrolled participants will also undergo blood sampling for evaluation of CMI responses. For further details relating to the booster assignments, please refer to the protocol.

Participants who complete study procedures through Day 98 will be offered the opportunity to determine if they are eligible for study re-enrollment to ensure dosing with ARCT-021.

After Day 98 and until Day 198, participants will be contacted to determine whether they are interested, if eligible, in re-enrolling in the study in order to receive active study vaccine. Only participants who are assigned to Study Group 4 (placebo) may re-enroll into the study.

Participants who received ARCT-021 of any dose (Study Groups 1, 2, 3) are asked to remain on the study schedule. Those participants who choose to re-enroll into the study complete early termination procedures and are assigned a new participant number when they re-enter the study. For this interim analysis, the data from re-enrolled participants is not included.

Vaccine doses for primary vaccination will be assigned as shown in Table 3-1.

Table 3-1 **Study Group Assignments**

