9.1.2.2. Unsolicited AEs by Time Period

Summaries of unsolicited AEs by time period will be presented using the following definition:

- **Prior to Booster Vaccination** summary tables include the following time periods with data summarized by the 4 priming vaccination treatment groups:
 - **Vaccination 1 through prior to Vaccination 2:**

- For participants who receive vaccination 2, this is the time period from first vaccination through prior to second vaccination
- For participants who do not receive vaccination 2 but do receive a booster vaccination, this is the time period from first vaccination through prior to the booster vaccination
- For participants who only received the first vaccination, this is the time period from first vaccination until early termination or end of the priming period (Day 207), whichever is earlier
- **Vaccination 2 through prior to Booster Vaccination:**
 - For participants who receive the booster vaccination, this is the time period from the second vaccination through prior to the booster vaccination
 - For participants who do not receive the booster vaccination, this is the time period from second vaccination until early termination or end of the priming period (Day 207), whichever is earlier
- **Prior to Booster Vaccination - Overall**
 - This is the time period from first vaccination through prior to booster vaccination. For participants who do not receive a booster vaccination, this is the time period from first vaccination through early termination or end of the priming period (Day 207), whichever is earlier.
- **Post Booster Vaccination through Early Termination** summary tables include data summarized by the 8 priming-booster treatment groups as well as a summary for the combined E1+E2+...+G1+G2 and H1+H2 groups. For subjects who do not receive a booster vaccination, this is the time period from the start of the booster period (Day 208) through early termination.
 - An overall summary of unsolicited adverse events post booster vaccination with active boosters pooled (as presented in Table 4-1; e.g., A1, A2, B1, B2, etc.) will also be presented.

The summaries described in [Section 9.1.2.1](#) will be produced by time period and by time period and age group. In addition, the following summaries will be presented by time period and by time period and age group:

- Overall summary and incidence of treatment emergent MAAE
- Overall summary and incidence of treatment emergent NOCDs

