9.4. COVID-19 exposure and symptoms

The number and percentage of participants reporting symptoms of potential COVID-19 (Yes/No/missing) from CRF page SARS-CoV-2 or COVID-19 Symptoms Assessment will be summarized by treatment groups for the Safety analysis set. For participants reporting ‘Yes’, all symptoms will also be summarized by frequency.

For participants identified as on-study infection, the number and percentage of participants reporting ‘Yes’ to the question Any Symptom of Confirmed COVID-19 from CRF page Clinical Event of Special Interest will be reported by treatment groups and by each priming vaccination period. All symptoms will also be summarized by frequency.

Incidence of COVID-19 and incidence of asymptomatic infection based on the Adverse Event CRF page will be summarized for the following time periods: after first study vaccine dose to 14 days after first study vaccine dose, between 14 days after first study vaccine dose to 2nd study vaccine dose, and after 2nd study vaccine dose to booster vaccine / early termination prior to Day 208 visit. This will also be summarized for re-enrolled subjects separately.

Incidence of COVID-19 and incidence of asymptomatic infection after booster vaccine to early termination after booster vaccine based on the Adverse Event CRF page will be summarized. For subjects not receiving a booster vaccination, events from Day 208 through early termination will be summarized under the Booster Placebo/No Booster group.

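### Late pre-booster safety and COVID-19 summaries are crude percentages of everyone treated, although only placebo participants can leave original follow-up by re-enrolling from Day 98

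*SAP*

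**What the plan says.** **Denominator.** SAP 9.1.2 states: "Percentages will be based upon the number of participants in the Safety analysis set within each treatment group". SAP 4.4.6 defines the Safety set as everyone with at least one priming dose, with no condition on follow-up. SAP 9.4 gives no denominator for the incidence of COVID-19 and asymptomatic infection. However, SAP 9 opens by placing all safety summaries on the Safety sets, and the general rule in SAP 4 divides by the treatment group's number in the analysis set.

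**Who can leave.** SAP 3.1: "Only participants who are assigned to Study Group 4 (placebo) may re-enroll into the study". The window is Day 98 to Day 198. Under Protocol 5.1 re-enrolling participants "will undergo Early Termination Visit, will be assigned a new participant ID number, and will re-enter the study at Day 0". Under Protocol 7.6.7 their safety data after active vaccination "will be summarized and presented by dose group and overall separately from those participants who complete the study as originally randomized".

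**Periods that run past Day 98.** SAP 9.1.2.2 summarizes MAAEs, NOCDs, SAEs and AEs leading to discontinuation/withdrawal from Vaccination 2 to booster, and overall before booster. For participants without a booster the overall period is defined thus: "this is the time period from first vaccination through early termination or end of the priming period (Day 207), whichever is earlier". In SAP 9.4 the third priming COVID-19 period runs "after 2nd study vaccine dose to booster vaccine / early termination prior to Day 208 visit".

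**Status of the endpoint.** The primary safety endpoint in Protocol 2.1 includes any MAAE, NOCD, "AE leading to discontinuation/withdrawal or serious adverse event (SAE) through Early Termination".

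**The concern.** Re-enrollment is an exit route built into one arm. A placebo participant who takes it at Day 98 contributes 70 of the 180 days from Day 28 to Day 208, yet counts as a full unit in the denominator. ARCT-021 participants who ask to re-enroll are told to stay on schedule.

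With no true difference between arms, the late-period tables would then tend to show more MAAEs, NOCDs and SAEs on vaccine, purely because vaccine recipients were watched for longer. In the COVID-19 table the same mechanism would hide part of any benefit.

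Protocol 3.1.1 defends the Day 98 start on the ground that "Targeting earliest re-entry after Day 98 allows for approximately 4 months of safety comparison in these participants". The final-analysis SAP nevertheless has no summary cut at Day 98. The interim analysis plans are separate documents that were not available, so nothing is said about them, nor about the DSMB's review or dose selection.

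**Working it through.** **Inputs from the documents**
- Late period: Day 28 to Day 208, 180 days. Overall pre-booster period: Day 0 to Day 208, 208 days.
- Re-enrollment possible from Day 98 to Day 198, placebo only.
- Planned placebo group: 75 per age cohort, so 2 × 75 = 150 (SAP 4.2).

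**Assumptions (not in the documents)**
- A fraction r of placebo re-enrolls, r = 10, 25, 50, 75%, all on day d = 98, 148 or 198. Day 148 is the middle of the window; Days 98 and 198 are its ends.
- The same constant hazard in both arms, giving a 10% risk over the full period.
- Complete follow-up in ARCT-021 (relaxed in step 5).
- The plan outputs no risk ratio; the ratio is used here only to size the gap.

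**1. The plan's own safety figure.** SAP Table 4-2 uses 1 − (1 − R)^N. At R = 1% this gives 22.2% (N = 25), 52.9% (N = 75), 77.9% (N = 150) and 95.1% (N = 300), matching the table. Those figures treat N as fully observed.

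**2. Vaccination 2 to booster.**
- h = −ln(0.9)/180 = 0.000585 per day.
- Risk accrued by a re-enroller before leaving: 1 − exp(−h(d − 28)), which is 4.01% at Day 98, 6.78% at Day 148 and 9.47% at Day 198.
- Crude placebo risk = (1 − r) × 0.10 + r × that risk. Ratio = 0.10 / crude placebo risk.
- Example, r = 50% at Day 148: 0.5 × 0.10 + 0.5 × 0.0678 = 0.0839, and 0.10/0.0839 = 1.19.

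| Re-enrolling | All at Day 98 | All at Day 148 | All at Day 198 |
|---|---|---|---|
| 10% | 1.06 | 1.03 | 1.01 |
| 25% | 1.18 | 1.09 | 1.01 |
| 50% | 1.43 | 1.19 | 1.03 |
| 75% | 1.81 | 1.32 | 1.04 |

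Ignoring the few days lost after an event, placebo mean follow-up at Day 148 is 180 − 60r = 174, 165, 150 and 135 days, against 180 in ARCT-021. Under these assumptions the ratio of events per person-time is 1.00 in every cell.

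**3. Overall pre-booster period.** The same formula over 208 days from Day 0, exit at Day 148, gives 1.03, 1.07, 1.16 and 1.26.

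**4. Expected events.** In 150 placebo participants, full follow-up yields 15. With exit at Day 148 this falls to 14.5, 13.8, 12.6 and 11.4. The Clopper-Pearson 95% interval for 15/150 is 5.7% to 16.0%, so the 50% case (8.4% instead of 10%) lies well inside it.

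**5. Offset.** If ARCT-021 participants also leave at Day 148, the 50% placebo case falls from 1.19 to 1.10 (25% of ARCT-021 leaving) or 1.00 (50% leaving).

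**6. COVID-19.** With a 10% placebo risk and a true halving of the hazard, ARCT-021 risk is 1 − exp(−0.5 × h × 180) = 5.13%. With half of placebo leaving at Day 148, the crude reduction is 1 − 0.0513/0.0839 = 39%. With half leaving at Day 98 it is 1 − 0.0513/0.0701 = 27%.

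**7. Does other text correct this?**
- SAP 4.6 ties percentages to the period of interest, but the late period opens at dose 2, before anyone can re-enroll, so re-enrollers remain in it.
- SAP 5.1 tabulates discontinuation with reasons, separate disposition for re-enrolled participants, and broad follow-up bands (the priming-only band is under 12 months). It gives no time at risk.
- SAP 1 warns of limited interpretation beyond Day 56, citing attrition and other vaccines, and plans no correction.
- Neither document plans a person-time rate or a time-to-event method for these events.

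**The case against.** The strongest defense is that the SAP delivers what the protocol defined. The endpoint is a number and percentage of participants, Estimand 1's summary is a percentage of those vaccinated, and Protocol 7.2 rules out hypothesis testing. That is so: no error rate is affected and no text is contradicted. But the objective is safety compared with placebo, and readers will compare the columns.

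The size is hypothetical. At Day 148, 10% to 50% re-enrolling costs 0.5 to 2.4 of 15 expected events, within sampling error, and ARCT-021 exits could cancel it. This stands and limits the severity. A wide interval does not remove a directional bias, though, and no planned table would show whether the exits balance.

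Re-enrollers may also be lower-risk. Protocol 5.1 admits only those who have not met withdrawal criteria for study vaccine, and these include related SAEs and severe related events. Fewer events would then be lost than computed here, and censoring at re-enrollment would be informative. This stands as a caution on person-time rates; a summary cut at Day 98 avoids it.

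The disposition tables already show part of the attrition. They describe it without adjusting any incidence, and they omit time at risk by arm.

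Finally, SAP 9.4 names no denominator for COVID-19 incidence. The opening of SAP 9 and the general rule in SAP 4 supply one. COVID-19 incidence is exploratory, so the primary-endpoint argument applies only to the AE tables.

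**Conclusion.** The concern holds. As written, the plan lets follow-up shorten in the placebo arm alone through re-enrollment, while dividing by everyone treated. It affects the two late pre-booster AE summaries, which bear on a primary safety endpoint, and the third priming COVID-19 period. The 7-day and 28-day tables (the latter cover SAEs, MAAEs, NOCDs and discontinuations to about Day 56) and the first two COVID-19 periods are not affected.

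The direction is toward understating placebo incidence relative to ARCT-021, unless other exits offset it. The size ranges from negligible (re-enrollment near Day 198) through 1.03 to 1.32 (Day 148) to 1.81 in the extreme case of 75% leaving at Day 98. These figures rest on an assumed re-enrolled fraction, a 10% risk, equal constant hazards and complete ARCT-021 follow-up. Because the analysis is descriptive and the size unknown, this should be corrected but does not invalidate the safety analysis.

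**What to change.** In SAP 9.1.2.2 and 9.4, for the affected late-period summaries only:

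1. Add events per person-time at risk by arm with 95% confidence intervals, censored at re-enrollment, booster or exit.
2. Add one summary truncated at Day 98 in all arms.
3. Tabulate follow-up time and reason for end of follow-up by arm, with re-enrollment as its own category.
4. Keep the crude percentages alongside.

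The cost is SAP wording and a few tables from dates already collected. The Day 98 cut will contain fewer events. Person-time rates assume non-informative censoring, which may fail if re-enrollers differ in risk, and the SAP should say so.

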9.1.2.1. Unsolicited AEs through 28 Days Post Each Vaccination

Summaries of unsolicited AEs through 28 days post each vaccination dose will be presented using the following definition:

- **Vaccination 1:** Time period from first vaccination through prior to the second vaccination for participants that received the second vaccination and through 28 days following the first vaccination for participants that did not receive the second vaccination
- **Vaccination 2:** Time period from second vaccination through 28 days following the second vaccination
- **Booster Vaccination:** Time period from booster vaccination through 28 days following the booster vaccination.

The summaries for Vaccination 1 and Vaccination 2 will be by the 4 priming vaccination treatment groups for the priming vaccination period while the summaries for booster vaccination period will be by the 8 priming-booster vaccination treatment groups and for the combined E1+E2+...+G1+G2 and H1+H2 groups (Table 4-1).

For re-enrolled subjects, the above summary for the priming vaccination phase will be repeated.

An overall summary of unsolicited AEs through 28 days post vaccination will be produced for all participants and by age group including the number and percentage of participants with any of the following (including 2 sided 95% CIs using the Clopper-Pearson method):

- Any unsolicited TEAEs
- Any severe unsolicited TEAEs
- Any unsolicited TEAEs that are treatment related

- Any severe unsolicited TEAEs that are treatment related
- Any serious TEAEs
- Any treatment-emergent MAAEs
- Any treatment-emergent NOCDs
- Any TEAEs leading to discontinuation/withdrawal
- Any TEAEs leading to death

In addition, incidence of unsolicited AEs through 28 days post each vaccination will be summarized by SOC and PT including number and percentage of participants with an event for all participants and by age group for the following:

- All unsolicited AEs
- All unsolicited AEs by severity
- All unsolicited AEs by relationship to treatment

For re-enrolled subjects, the above summaries will be repeated for the Safety set. A summary of incidence of unsolicited adverse events up to 28 days post booster vaccination with active boosters pooled will be presented.

Incidence tables will be presented by SOC and PT with counts of participants included. SOC will be displayed in internationally agreed order. PT will be displayed in descending order of frequency of treatment group and then alphabetically within SOC. When summarizing the number and percentage of participants with an event, participants with multiple occurrences of the same AE or a continuing AE will be counted once. Only the maximum severity level will be presented in the severity summaries, and the strongest relationship level will be presented in the relationship summaries. If the severity information is missing, the AE will be considered severe in the summary, but the severity will be presented as missing in the data listings.

